7.7.7 Family Functioning (Hypothesis 2e)

Hypothesis 2e: BSFT will be significantly more effective than TAU in improving family functioning.

- Parenting Practices Questionnaire of The Chicago Youth Development Study. *Parenting practices* will be measured through 47 questions on parent and adolescent reports (Gorman-Smith, Tolan, Zelli, & Huesmann, 1996). The Parenting Practices Measure, was derived from the parental supervision and discipline interview used in the Oregon Youth Study and Pittsburg Youth Study (Thornberry, Huizinga, & Loeber, 1995). Factor analyses have identified four factors 1) Positive Parenting, 2) Discipline Effectiveness, 3) Avoidance of Discipline, and 4) Monitoring. Positive parenting refers to the use of positive rewards and encouragement of appropriate behavior. Discipline effectiveness is a measure of how effective parental discipline is in controlling the youth's behavior. Avoidance of discipline refers to the parent's avoidance of providing consequences or disciplining for fear of the youth's behavior escalating. Monitoring is a measure of monitoring and involvement in daily activity and routines and knowledge of youth's whereabouts throughout the day. Reports of discipline effectiveness and avoidance of discipline are gathered from parents only. Estimates of positive parenting and extent of monitoring are gathered from both parent and child. Internal consistency reliabilities of each of the subscales ranged from .68 to .81. Confirmatory factor analyses have consistently identified two latent constructs of Discipline and Monitoring which will be the two indicators of parenting used in the family functioning composite (Gorman-Smith et al., 1996). All four factors in this inventory will be used as indicators of parenting practices.
- Family Environmental Scale. The Family Environmental Scale (FES; Moos & Moos, 1986) is a widely used measure that was developed to measure social and

environmental characteristics of families. This measure has been used in thousands of studies to capture critical aspects of family functioning. In this study, we will be using the cohesion and conflict subscales of the FES, administered to both parents and adolescents. Internal consistency reliability estimates for the subscales range from 0.61 to 0.78. Conflict and cohesiveness subscales will be administered to measure family functioning.

7.7.8 Adolescent and Parent Psychiatric Functioning (Planned Post-Hoc Analyses)

Measures of adolescent and parent psychiatric functioning are included to provide information that is useful in interpreting and reporting results. These variables may be used as potential covariates in the analyses.

- Diagnostic Interview Schedule for Children-Predictive Scales. This measure will be used at baseline to identify the probability of the *presence or absence of 13 psychiatric disorders—Simple Phobia, Social Phobia, Agoraphobia, Panic Disorder, Avoidant Disorder, Generalized Anxiety Disorder, Obsessive-Compulsive Disorder, Major Depressive Disorder, Mania, Psychotic Disorder, ADHD, Oppositional Defiant Disorder, and Conduct Disorder*. This measure is administered to both youth (98 items) and parents (92 items) to assess the adolescent’s psychological functioning. This instrument has demonstrated excellent sensitivity and specificity compared to the full Diagnostic Interview Schedule for Children (Lucas et al., 2001). Research Assistants will be trained to refer cases to the Clinical Supervisor in the event that adolescents and parents answer positively for psychotic symptoms or threshold Major Depressive Disorder. In these cases, further assessment will be offered in accordance with standard CTP practice. However, for this protocol these symptoms will not be considered AEs.

7.7.9 Adolescent Internalizing Problems (Planned Post-Hoc Analyses)

Internalizing problem measures were selected to provide information that is useful for interpreting and reporting results.

- Youth Self Report (Achenbach & Edelbrock, 1991). The broad – band *Internalizing factor* from this measure will be used as an indicator of internalizing problems (measure describe above). In the event adolescents answer positively to the question: I deliberately try to hurt or kill myself, the Research assistant will refer the adolescent to the Clinical supervisor for further evaluation for suicide risk
- Diagnostic Interview Schedule for Children-Predictive Scales. *Internalizing disorders (Phobia, Panic, Avoidant Disorder, GAD, OCD, and MDD)* will be identified using both parent and adolescent report (measure described in 7.7.3).

7.7.10 Parent Functioning (Planned Post-Hoc Analyses)

The ASI-Lite is included in this battery because it provides information about parents’ functioning that is useful for interpreting and reporting results.

- Addiction Severity Index-Lite. The Alcohol and Drug Use items from the Addiction Severity Index-Lite (Common Assessment Battery) will be administered to participating primary parent or caregiving figure to assess parent alcohol and drug use.

7.7.11 Adverse Events

- Adverse Events/Serious Adverse Events. A general inquiry method will be employed to identify AEs/SAEs (Jacobson, Goldstein, Dominguez, & Steinbook, 1987; Levine & Schooler, 1986) by the Research Assistants. Scheduled inquiries by the non-blind

research assistant will occur at each B1, T2, T4, T8, and T12. However, identification of AEs/SAEs may occur at any point in the project. Often, AEs/SAEs will be identified by therapists if the participant or family members bring them up in the sessions. The Research Assistant blind to condition and who performs drug use outcomes will also identify SAEs and AEs during the monthly assessments with adolescents. Research assistants and therapists in both conditions will be trained to identify adverse events and serious adverse events as defined in this protocol. All AEs/SAEs will be documented by project staff (research assistants responsible for secondary outcomes and other appropriate site research staff) using the Adverse Events CRF designed for this protocol (see Appendix B).

7.7.12 Clinical Forms for BSFT (see Appendix B)

- Clinical Contact Log. A contact log will be completed to document every therapist-participant contact, including telephone calls and therapy sessions. This form identifies the type of contact (e.g., individual therapy, family therapy, group therapy, telephone call) as well as general information about the contact (e.g., who participated, length, location, date). A sample of this form is included in Appendix B. A copy of this form will be sent to the Florida Node at the end of each week for the purpose of supervision.
- Weekly Case Summary. BSFT therapists will complete a Weekly Case Summary Form (Appendix B), which will be updated every week. This form documents the level of severity of specific family problems that are targeted for treatment as well as the amount of focus directed to each problem every week. This form is used for the purpose of supervision, and as such, for each participant/family, a copy will be sent to the Lead Node at the end of each week.

7.8 Administration Time

The baseline assessment takes approximately 3 hours to complete for the adolescent, and approximately 1.25 hours for parent(s)/guardian(s). Follow-up assessments take approximately 2.5 hours for the adolescent and 1 hour for parent(s)/guardians(s).

7.9 Reimbursement

Participants will be reimbursed for their completion of scheduled secondary outcome assessments. All payments will be made to parent(s)/guardian(s) at the completion of each assessment. For the completion of secondary outcome measures the parent /guardian will receive \$25 at B1, \$35 at T4, \$45 at T8, \$55 at T12. The total payment recommended for a participant family is \$160. All payments will be made directly to the parent figures/guardians participating in the assessment. Adolescents will receive approximately \$10 in movie tickets or a similarly valued incentive for the primary outcome assessments (B1, T1 T12)

Sites may include additional compensation to reimburse participants for transportation costs to and from the assessment location. The amount of additional compensation will be determined by each CTP and must be approved by the corresponding IRB. Participants will not be compensated for therapy sessions.

7.10 Pilot Cases

Pilot participants will be recruited to participate in testing the procedures for all aspects of the study. Pilot participants may participate in all or a specific aspect of the study. For example, a pilot participant may only be involved in piloting one of the baseline measures.

With respect to pilot cases, the only requirements for enrollment and consent are that the adolescent be between 12-17 years of age (inclusive) and that they live with an adult (over 21 years old) parent figure. These requirements apply for piloting any aspect of the study (BSFT or assessment measures). However every effort should be made to pilot participants as close as possible to the study inclusion-exclusion criteria. All pilot participants should be consented to participate in the pilot phase.

Pilot participants will also be tracked for AE/SAEs.

8.0 ASSESSMENT AND REPORTING OF ADVERSE EVENTS

Adolescent and family member responses on assessments will be kept strictly confidential. The only exceptions are in cases of imminent danger, including suicidality, homicidality, abuse or neglect.

8.1 Assessment of Adverse Event Severity and Relationship to Treatment

Based on our experience implementing BSFT, we have identified common AEs and SAEs for this population; these will be reported during protocol. The events are defined in Table 2.

Table 2. Family Participants

Adverse Events

1. Arrest
2. Runaway
3. Kicked out of Home
4. School Suspension/Expulsion/Dropout
5. Violence (Victim/Exposure)

Serious Adverse Events

6. Physical/Sexual Abuse
7. Suicidal Behavior
8. Homicidal Behavior
9. Hospitalization (psychiatric, drug related)
10. Death

Unexpected Adverse event 11. Other (indicate if serious)

Adverse events for this study may be identified during regularly scheduled intervals or may be reported at any other times during the study. For adolescents and their parent /guardians that are participating in assessments, the ten adverse events listed above (see Table 2) will be queried specifically at T4,T8,T12 time points. An “other” category has been included to allow sites to capture unexpected adverse events reported by participants which do not fall within the scope of any of the ten defined AEs/SAEs for this protocol. All 13 assessments conducted by the blind research assistant are opportunities for identifying adverse events if reported by the participant. All research assistants conducting primary and/or secondary outcome assessments, will be trained to identify AEs and SAEs at each of these time points. Additionally, anytime during the study, a participant or his/her family member may report an AE. These events will be identified, classified as serious or not, and notified by the therapists or RA- blind to the RA –non blind and will be handled in the same manner like AEs during the formal assessments. In the event that any other person reports an adverse event for the adolescent, the research team must find out with the legal guardian or the adolescent about the occurrence of the event.

Both, TAU and BSFT therapists will be trained to identify adverse events, and categorize serious adverse events, based on direct reporting during sessions. Upon identification of an adverse event, all research team (blind RA, non-blind RA, and therapists) should categorize the event for seriousness to guarantee that appropriate care and reporting occurs within approximately 24 hours. As soon as any adverse event is identified, either by querying or direct report, the event will be recorded in the AE CRF by the non-blind research assistant. In addition, the Clinical Supervisor at the site will be notified of any and all AEs. All non-serious AEs will be handled based on standardized operation procedures at the site. In both treatment conditions, action may be taken by the therapist to respond to

non-serious events (e.g., booster sessions, or increase in the frequency of sessions). If therapists or blind research assistant were the ones to identify the events, after notifying the Clinical Supervisor, they are to notify and inform the non-blind research assistant, who is then responsible for conducting further evaluations and completion of the AE CRF. All non-serious adverse events require no further reporting. All AE CRFs will be reviewed by the CTP PI weekly to evaluate relatedness to the intervention and resolution.

If the event is categorized as serious, the reporting procedures for SAEs experienced by any participant in the BSFT trial will be in accordance with the CTN Medical Safety Monitoring Policy. In the occurrence of a SAE, the Clinical Supervisor and the CTP PI must be notified when possible within 2 hours of identification. The non-blind research assistant will be responsible for recording the event in the AE CRF. The Clinical Supervisor will be responsible for ensuring care of participants, based on standardized operating procedures at the site. The CTP PI will then be responsible for assessing the event's "relatedness to the intervention".

For SAEs, an initial telephone report will be made to NIDA/CCTN Medical Monitor for BSFT, the Node PI, the Lead Node Project Director ([name]) and the Lead Investigator ([name]) at the University of Miami Center for Family Studies. The CTP PI will be responsible for completing and faxing the SAE form report within 24-hours of identification to the NIDA/CCTN Medical Monitor for BSFT, the Node Study PI, the Lead Node Project Director ([name]) and the Lead Investigator ([name]) at the University of Miami Center for Family Studies. The research staff will also contact the same parties listed above, to ensure that paperwork is received and proper notifications are made.

The Lead Investigator ([name]) in collaboration with the BSFT Medical Officer ([name]) will then be responsible for completing a final written SAE summary report. Completions and submission of the Summary Report to the NIDA medical office will be done within 2 weeks of notification. The NIDA/CCTN Medical Monitor for BSFT will then inform the DSMB. The BSFT Project Director ([name]) will forward the LI Summary Report to the Lead Node IRB (UM IRB) as well as to other CTPs and Nodes, with a request that they report to the respective IRBs involved. The CTP PI, the NODE PI, and the Lead Investigator will track all SAEs until resolution has been achieved. Follow-up reports will be sent by the CTP PI to the LI on a monthly basis. However, if any relevant follow-up information is learned about the SAE this must be reported to the LI as soon as the CTP PI becomes aware. SAE summary reports on follow-ups will be submitted to NIDA on a quarterly basis.

In this study, therapists are also considered research participants. However, therapists are not the target of the intervention. As such, therapists are not directly influenced by the intervention. Nonetheless, there may be negative consequences for therapist participants in this protocol. All of these consequences are job-related. Three AE/SAEs for therapists will be identified, recorded and reported. These include 1) any injury that is sustained on the way to, during, or on the way back from a therapy session, 2) death, and 3) other event identified by the Site Principal Investigator or Site Clinical Supervisor. These risks as well as confidentiality issues are included in the consent forms and procedures. Reporting of adverse events for therapists will follow the same guidelines as for participants in the study.

[figure not shown]
8.2 Monitoring Adverse Events

As depicted in Figure 2, AEs may be tracked and identified in three ways: 1) the research assistant will inquire and document the occurrence of the listed events during the assessment at B1, T4, T8, T12; 2) the blind research assistant will identify upon self report at all 13 monthly primary outcome assessment points, and/or 3) the adolescent and/or family may report the listed events during scheduled or unscheduled contacts. If an AE is identified, the adolescent will be referred to the

[name]

research assistant- non blind for further assessment of AEs. The assessment and logging of the AE CRFs will be performed by the research assistant responsible for the secondary outcomes assessments. This is to ensure blindness to condition by the blind research assistant. Likewise, if the therapist identifies the adverse event, the participant will be referred to the non-blind research assistant for further assessment. Therapists (both BSFT and TAU) and research assistants will notify the Clinical Supervisor of all AEs. For SAEs, therapists and research assistants will notify CTP PI and Clinical Supervisor within approximately two hours of identification. For all events identified in either the assessment or through therapy contacts, the non-blind Research Assistant is responsible for completing the AE CRF except for evaluation on severity, relatedness to the intervention and resolution status. The latter are the responsibility of the CTP PI. For SAEs, the CTP PI is responsible for completing the SAE Form and notifying the NIDA representative and the LI within 24 hours (via fax or phone). The LI (or Study MD) will complete an SAE Reporting Form and a summary report for every SAE. SAE Summary Reports must be submitted to NIDA within 2 weeks of notification.

Figure 2: AEs & SAEs Identification, Assessment and Report
Research Assistant- Non Blind (T0, T2, T4, T8, T12)

Note: * Research Assistant blind to condition will be trained to identify AEs in the event they are communicated during drug use assessments by the adolescent. In this event, they will refer the adolescent to the Research Assistant responsible of the assessment of secondary outcomes.

Each week the CTP PI must review all of the AE CRFs completed during that week – 1) to determine the study-relatedness of all AEs/SAEs, and 2) to track the current status of all unresolved SAEs. All SAEs will be tracked by the CTP PI and the LI (or protocol Medical Officer) monthly until a satisfactory resolution is achieved. Tracking and resolution parameters for each SAE are described below. It should be noted that non-serious AEs will not be tracked to resolution.

8.3 Serious Adverse Events

SAEs include 1) Physical/Sexual Abuse, 2), Suicidal Behavior, 3) Homicidal Behavior, 4) Hospitalization (psychiatric or drug related), and 5) Death.

All of these problems may involve imminent danger to self or other. In cases of current suicidal, homicidal, and abusive behaviors, participants in both BSFT and TAU will be immediately referred to the clinical supervisor to ensure that appropriate crisis intervention services are provided. Each of the CTPs that have expressed interest in this protocol has a procedure in place for managing these emergencies. Serious adverse events listed in this study will also be reported for any family participant. However, these cases will not be withdrawn from the study. Adequate medical care of family members, like with the adolescents, will be provided following the SOPs at each CTP.

1) Physical /Sexual Abuse

Any injury inflicted by hitting, kicking, burning, shaking or throwing (etc.) that result in bruises, marks or injuries, that require medical attention should be considered physical abuse. The CTP Clinical Supervisor is responsible for the ultimate safety of adolescents and family members in the case of family therapy, in both conditions. As such, the CTP Clinical Supervisor will oversee the implementation of the CTP procedures for handling physical abuse. These procedures will be handled identically in both conditions. However, in BSFT, our experience with drug abusing adolescents is that for the vast majority of cases, an intensification of intervention dosage is sufficient to overcome the crisis. BSFT therapists will work with the BSFT Clinical Supervisor and the CTP Clinical Supervisor to ensure that both CTP and BSFT implementation parameters are applied appropriately. In those cases in which the situation is exceptionally intense / dangerous, a strategy we have used successfully is to arrange a respite for the family members. One step in achieving such a respite is to work with extended family to arrange for the potentially violent individual to stay with extended family for a few days, although all members continue to be active in therapy and work through the critical family issues. In extreme cases in which no family members or kin are available as resources for the family, we have successfully used community shelters where the adolescent can stay in a non-therapeutic but safe environment. Conjoint therapy sessions continue during this period of respite providing continuity to the treatment. CTPs have considerable experience negotiating difficult situations such as potential violence. Although CTPs are less likely to utilize the solution of placing adolescents with extended family members, CTPs may link family members to community shelters or seek other mechanisms to protect individuals from harmful situations. This does not require the adolescent's withdrawal from the study because in many cases it is the caregiver/parent figure who is asked to leave the home in which the adolescent resides—or the adolescent may be placed temporarily in a shelter where they are not at immediate risk. Adolescent will be withdrawn from the study only in cases in which contact with any potential caregivers is proscribed.

Any reports of sexual abuse by adolescents or family members will require a legal report. As noted above, the CTP Clinical Supervisor is responsible for the ultimate safety of adolescents in both conditions. As such, the CTP Clinical Supervisor will oversee the implementation of the CTP procedures for managing and reporting sexual abuse. This is likely to include additional interviewing, scheduling pediatric consultations, as well as the potential placement of the alleged perpetrator or

[name]

victim outside of the home. Again, the CTPs procedures for managing such events will be maintained in both conditions. However, BSFT therapists will also implement family-focused interventions. Like in cases of physical abuse, an intensification of intervention dosage is often required. During this type of crisis, BSFT therapists may work with family members to process anger and shame that family members may feel after the disclosure of abuse. This anger is often directed toward the individual that “betrayed” the family by sharing this secret. The BSFT therapist attempts to gather information about the short- and long-term consequences (e.g., legal, home composition) of this report, and design and implement interventions that facilitate adaptive family coping responses and minimize the negative impact on the target adolescent.

2) Suicidal Behavior

Suicidal behaviors include any risk or attempt to inflict serious bodily harm to self that may result in death. The typical procedure at CTPs in cases of adolescent suicidal behaviors is to refer the adolescents for an evaluation by a licensed mental health provider, preferably a psychiatrist. However, based on the services available within the CTP and in the community, the specific nature of services that adolescents may receive for the treatment or stabilization of suicidal behaviors may vary. All suicidal behaviors will be referred to the CTP Clinical Supervisor who will conduct an evaluation to determine the need for additional emergency psychiatric consultation and/or hospitalization. In our discussions with CTP representatives on the Protocol Development Team, we have identified that the following examples are common in the CTPs responses to and evaluation of suicidality. Evaluation should be made of: a) the circumstances (emotional and social) preceding or following the suicidal behavior, b) history of impulsive behavior, c) wishes to die or to influence others at the time of the attempt, and d) whether a friend or a family member has committed suicide. The nature of the behavior should be considered as an indicator of intent: accidental discovery versus attempt in the views of others or telling others immediately, careful plans to avoid discovery, hanging or gunshot. Hopelessness, regret at being rescued, belief that things would get better for self or others if dead, wish to rejoin a loved one, belief that death is temporary and pleasant and unwillingness to call before attempting suicide are considered indicators of intent to die. Due to high clinical risk in these patients it is expected that clinical consultation by a psychiatrist will result in hospitalization for attempts and for ideation with a plan and intent to die.

3) Homicidal Behavior

Homicidal behaviors include any attempts to seriously injure or kill another person. Homicidal behaviors also include any ideations (e.g., thoughts/intentions) that are considered to represent a legitimate threat to another person. All homicidal behaviors will be referred to the CTP Clinical Supervisor who will conduct an evaluation to determine the nature of the behaviors, including the legitimacy of the threat. When necessary, the CTP Clinical Supervisor is responsible for notifying the appropriate authorities as well as the potential victim that is identified by a legitimate threat. Adolescent participants with homicidal behaviors will be withdrawn from BSFT. BSFT services may be reinstated when the homicidal behaviors are no longer present. Adolescents and family members will continue to receive study assessments.

4) Hospitalization (psychiatric or drug-related)

Given the chronic nature of drug abuse as well as the high incidence of psychiatric comorbidity among adolescent drug users, we expect that some youth may require hospitalization for psychiatric or drug-related reasons during the protocol. All hospitalizations for psychiatric or drug-related reasons will be reported to the CTP Clinical Supervisor.

When an adolescent is placed in a more restricted environment during the treatment phase of BSFT, therapists will contact the family each month to determine when the adolescent is expected to be released back to live with the family. When appropriate and permitted, family sessions will continue. For adolescents that are released back to live with the family prior to 12-months post-randomization, treatment (in the first 6 months) or “booster” sessions will be conducted with adolescents and family members to facilitate a smooth transition back into the home and to achieve or solidify improvements in family functioning and adolescent behavior problems.

5) Death

For adolescents in BSFT, deaths of primary caregivers and immediate family members (e.g., brother, sisters) that are participating in the intervention will be reported. As with all other SAEs, the CTP Clinical Supervisor is responsible for ensuring that therapists in both conditions follow standard CTP procedures for handling deaths. In BSFT, therapists are expected to conduct sessions with surviving family members to facilitate the family members’ adjustment and to make referrals to appropriate mental health services if necessary.

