4.7 Subject Discontinuation Criteria

4.7.1 Required Termination

Participants and family members will be terminated from the study when they state they no longer want to participate, hence, at the participant's request all assessments will be stopped. However, participants that are withdrawn from a treatment condition (i.e., stop attending treatment, or ask to discontinue treatment, or break the agency's rules) will continue to be included in the study, and assessments will still be conducted.

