4.7.2 Withdrawal of Participants

Adolescent and family members may be withdrawn from the treatment condition in the event the adolescent: a) attempts suicide with the intent to die, b) reports homicidal ideation with the intent to kill, or, c) dies.

It should be noted that removal from the treatment protocol does not mean removal from analysis. This is an "intent to treat" design. Therefore, every participant that is randomized will be analyzed.

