3. Kicked out of Home	Report	Structured QUESTIONING	NO	Increase frequency/dose of sessions, or booster sessions if therapy completed or other	None
4. School Suspension/Expulsion/Dropout	Report	Structured QUESTIONING	NO	Increase frequency/dose of sessions, or booster sessions if therapy completed or other	None
5. Violence (Victim/Exposure)	Report	Structured QUESTIONING	NO	Increase frequency/dose of sessions, or booster sessions if therapy completed or other	None
6. Physical/Sexual Abuse by family member	Report	Structured QUESTIONING	YES	Mandatory reporting to authority; Increase frequency/dose of sessions, or booster sessions if therapy completed or other	Report to LI and NIDA within 24 hrs
7. Suicidal Behavior	Report	Structured QUESTIONING	YES	Referral to psychiatrist or other	Report to LI and NIDA within 24 hrs
8. Homicidal Behavior	Report	Structured QUESTIONING	YES	Report to police, inform the victim. Referral to a psychiatrist or other. Withdrawal from the intervention	Report to LI and NIDA within 24 hrs
9. Hospitalization (psychiatric, drug related)	Report	Structured QUESTIONING	YES	None or other	Report to LI and NIDA within 24 hrs
10. Death	Report	Structured QUESTIONING	YES	Intensify work with Family in BSFT or other	Report to LI and NIDA within 24 hrs

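### Protocol sections 4.7.2, 8.3 and 8.5 give conflicting rules for stopping treatment after a homicidal event, and 8.3 ends study follow-up after abuse on a ground that 4.7 does not list

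*Protocol*

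**What the plan says.** **Homicidal events.** Protocol section 4.7.2 sets a general, permissive rule: "Adolescent and family members may be withdrawn from the treatment condition in the event the adolescent: a) attempts suicide with the intent to die". Its second ground is that the adolescent "b) reports homicidal ideation with the intent to kill".

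Section 8.3, item 3, defines the event more widely: "Homicidal behaviors include any attempts to seriously injure or kill another person". It also counts ideation judged to be a legitimate threat. The consequence is then stated for one arm: "Adolescent participants with homicidal behaviors will be withdrawn from BSFT". The same paragraph allows BSFT to resume once the behavior has ceased, and says that study assessments go on.

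The AE/SAE summary table in section 8.5 gives, as part of the clinical action for homicidal behavior, "Withdrawal from the intervention".

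**Abuse events.** Section 8.3, item 1, says: "Adolescent will be withdrawn from the study only in cases in which contact with any potential caregivers is proscribed". Section 4.7.1 gives the participant's own wish as the ground for ending study participation. It says that those withdrawn from a treatment condition "will continue to be included in the study, and assessments will still be conducted". Section 4.7.3 repeats this for people who drop out of therapy, unless they decline the assessments. Section 10.1.1 relies on continued assessment to keep missing data low.

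**The concern.** Site staff would turn to these sections in an emergency involving a minor. If the sections disagree on whether withdrawal is optional, what triggers it and which arm it covers, handling will depend on which page the site follows. Because one of the rules names BSFT alone, the difference can also fall along the randomized comparison. Treatment received, the engagement outcome of Hypothesis 2a (attendance at two or more sessions) and the adverse-event data shown unblinded to the DSMB could then differ between arms because of the rule itself.

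The abuse sentence raises a different problem. It ends participation in the study, not just in treatment, and so stops the monthly drug-use assessments that supply the primary outcome. It does so after a severe event that happens after randomization. The primary model assumes data missing at random, and section 10.2.1 adds only baseline predictors of missingness. Follow-up ended by such an event is a loss that the rest of the protocol tries to avoid.

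**Working it through.** No power, alpha or margin enters this point, and the plan states no figure to reproduce. The check is a comparison of the texts, followed by a count of assessments lost.

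**Step 1. Homicidal rules side by side.**

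| Source | Force | Arm | Trigger |
|---|---|---|---|
| 4.7.2 | permissive | treatment condition, so either arm | ideation with intent to kill |
| 8.3, item 3 | mandatory | BSFT only; no TAU action stated | attempts to seriously injure or kill, or ideation judged a legitimate threat |
| 8.5 summary table | listed with no discretion | not stated | homicidal behavior |

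The three sources differ on force, arm and trigger. Reinstatement appears only in 8.3, and only for BSFT. The table's term does not settle the arm, because section 5 uses the word intervention for both BSFT and TAU.

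**Step 2. Apply the rules to two cases.**

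- *An attempt to seriously injure someone, with no reported intent to kill.* Section 4.7.2 gives no ground for withdrawal. Section 8.3 requires withdrawal in BSFT and gives no withdrawal instruction for TAU. The table lists withdrawal, arm unstated.
- *Ideation with intent to kill, judged a legitimate threat.* Section 4.7.2 allows withdrawal in either arm. Section 8.3 requires it in BSFT. The table lists it, arm unstated.

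In both cases the outcome depends on the arm and on the section the site follows.

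**Step 3. Is the BSFT wording shorthand for both arms?** For physical abuse, 8.3 says that the site's procedures are applied identically in both conditions, and it says much the same for sexual abuse. No such statement goes with the homicidal withdrawal rule, so its extension to TAU cannot be assumed.

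**Step 4. Abuse rule against section 4.7.** Section 4.7.1 gives one ground for ending study participation (the participant's wish), and 4.7.2 lists grounds for leaving treatment. Neither includes barred caregiver contact. Sections 4.7.1, 4.7.3 and 10.1.1 all keep people who leave treatment under assessment. Item 3 of 8.3 also separates treatment from assessment, so item 1 is the exception.

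**Step 5. Follow-up lost per case.** There are 12 monthly post-randomization assessments (T1 to T12). An adolescent withdrawn after the month-m assessment loses 12 − m of them.

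- m = 1: 12 − 1 = 11 lost.
- m = 3: 12 − 3 = 9 lost, or 9/12 = 75%.
- m = 11: 12 − 11 = 1 lost.

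The whole trial plans 480 × 12 = 5,760 such assessments, so one adolescent withdrawn after month 3 accounts for 9/5,760 = 0.16%. The number of such adolescents is not given and could be zero.

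**The case against.** **On homicidal events**, 4.7.2 can be read as the general permission and 8.3 as the specific rule for BSFT. Section 8.3 first has the clinical supervisor assess how legitimate the threat is. TAU participants are not left without care: 8.3 sends participants in both arms to the clinical supervisor for crisis services, and some variation between sites in handling events is deliberate. Much of this stands as a description of care. It does not remove the conflict. The general-and-specific reading yields a stopping rule that differs by arm, and the table supports neither version clearly. A reader might also infer that this rule costs outcome data. It does not, because the same paragraph keeps assessments going.

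**On abuse events**, the sentence is a limit on withdrawal. It follows text saying that abuse does not normally require leaving the study. Its trigger is narrow, since family is defined broadly. It has a visible basis too: living with family is an inclusion criterion and a parent or guardian must consent. Section 4.7.1 does not say that its ground is the only one. All of this stands, and it makes the gap small. What remains is a ground for ending follow-up that 4.7 does not contain, in a protocol that elsewhere keeps treatment and follow-up apart.

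**Stronger readings that the text does not support.** A reader might infer that the abuse sentence drops adolescents from the intent-to-treat analysis. It does not say so. Section 4.7.2 has every randomized participant analyzed, and the likelihood model in 10.1.1 keeps cases with partial data. A reader might also infer that the suicidal-event rules contradict each other. Section 4.7.2 permits withdrawal after an attempt with intent to die, while 8.3 and the table describe evaluation, referral and expected hospitalization without mentioning withdrawal. The table entry leaves other action open. A permission and a silence can both be followed, so this is at most a mismatch by silence and is not part of the point.

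**Conclusion.** The protocol contradicts itself on homicidal events: three instructions differ on force, arm and trigger, so the same event can stop treatment in one arm or at one site and not in another. The consequence is for consistent handling of a safety event and for treatment exposure by arm, not for the collection of outcomes.

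The abuse sentence in 8.3 is out of line with 4.7.1, 4.7.3 and 10.1.1. It ends primary-outcome follow-up for those affected, up to 9 of 12 assessments if withdrawal comes after month 3, without removing anyone from the analysis. The protocol gives no event rate and the trigger is narrow, so the number may be very small and the effect on the primary estimate slight. Whether the missing outcomes could be treated as missing at random, given the drug use already observed, cannot be settled from the document, and a material bias is not shown. The point rests on the wording and needs no assumed rate. Which clinical rule is right is not judged here.

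**What to change.** Reconcile section 4.7.2, section 8.3 item 3 and the homicidal row of the summary table in section 8.5, so that the trigger, the degree of discretion and the arms covered are stated consistently in all three. The clinical content is for the sponsor and the DSMB to settle.

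Reconcile the abuse sentence in section 8.3 item 1 with section 4.7. The text should keep withdrawal from treatment separate from withdrawal from research follow-up, so that monthly drug-use assessments continue where consent and law permit. If some cases must still leave the study, list that ground in 4.7.

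The cost is a wording amendment and a memo to sites. Continued assessment after leaving treatment is already protocol procedure. The one practical matter to work through is guardian consent when caregiver contact is barred.
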